Study Design and Participants

This study was conducted as a randomized, sham-controlled, single-blind clinical trial to investigate the combined effects of Botulinum Toxin Type A (BTX-A) and Mirror Therapy (MT) on upper extremity spasticity in stroke patients. Ethical approval was obtained from the Institutional Review Biruni University Clinical Research Ethics Committee and all participants provided written informed consent prior to enrollment in accordance with the Declaration of Helsinki (2015-KAEK-80 23 50).

Participants were selected from the neurological rehabilitation clinic of the physical medicine and rehabilitation unit at Biruni University Hospital. Eligible patients were those diagnosed with unilateral ischemic stroke and scheduled to receive BTX-A injections for upper extremity spasticity management.

Inclusion criteria were as follows:

- Age \geq 18 years
- Diagnosis of unilateral ischemic stroke confirmed by neuroimaging (MRI or CT)
- At least 3 months post-stroke to ensure chronic phase status
- Routine follow-up under the care of the same clinician who determined BTX-A treatment indication based on established clinical guidelines
- Mini-Mental State Examination (MMSE) score > 24 to ensure adequate cognitive function for participation
- Fugl-Meyer Assessment (FMA) upper extremity motor score < 55 , indicating moderate to severe motor impairment
- Modified Ashworth Scale (MAS) score between 1 and 4 in the affected upper extremity, indicating presence of spasticity

Exclusion criteria:

- Prior BTX-A or other neurotoxin injections to the affected upper extremity within the last 6 months
- Severe cognitive impairment or psychiatric disorders interfering with communication or compliance
- Concurrent participation in other experimental rehabilitation or pharmacological trials

- Visual or motor deficits severe enough to prevent effective engagement with Mirror Therapy
- History of multiple strokes or bilateral brain lesions
- Presence of neuromuscular diseases affecting the unaffected upper extremity
- Stroke etiology other than ischemic (e.g., hemorrhagic stroke, traumatic brain injury)

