A total of 43 participants were initially enrolled between May 2024 and February 2025 from the neurological rehabilitation clinic of the Physical Medicine and Rehabilitation Department at Biruni University Hospital. Following baseline evaluations and BTX-A injections, participants were randomly allocated into two groups: 22 patients in the Mirror Therapy (MT) group and 21 patients in the Sham Therapy (SHA) group. Permuted block randomization was employed to ensure balanced group sizes and reduce selection bias. The randomization sequence was generated using a computer-based random number system and was implemented by an independent researcher not involved in patient assessment or treatment. Group allocation was concealed using sealed, opaque envelopes until the point of assignment.

In the MT group, 4 participants were excluded due to irregular attendance (<75% session compliance), 2 participant withdrew their informed consent, and 1 were hospitalized for unrelated medical conditions requiring inpatient treatment. In the SHA group, 4 participants failed to adhere to the intervention frequency, and 2 were excluded because they received additional pain management therapies during the follow-up period.

Consequently, 15 participants in each group (n = 30 total) completed the full 6-month intervention and follow-up assessments and were included in the final statistical analysis. The overall participant flow, including recruitment, allocation, and attrition, is illustrated in.

The study was conducted according to the approved protocol and completed as planned without early termination. The follow-up period for each participant lasted six months after BTX-A injection, and all post-treatment evaluations were completed by March 2025.

All intervention sessions were delivered by the same licensed physical therapist specialized in neurorehabilitation, ensuring procedural consistency across both groups. Adherence to the

intervention protocol was closely monitored by weekly attendance tracking and therapist supervision to maintain treatment fidelity.

Participants were allocated as follows:

- **Experimental Group (Group I, n=15):** Received mirror therapy in addition to conventional rehabilitation.

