- **Control Group (Group II, n=15):** Received a sham intervention alongside conventional rehabilitation. In this group, a transparent glass panel was used in place of a mirror, and patients were instructed to observe the reflection of their paretic extremity, thereby eliminating the visual illusion effect central to mirror therapy.

A single-blind study design was implemented to minimize bias. Neither the participants nor the outcome assessors were aware of group assignments. Both the mirror therapy and sham interventions were administered by a licensed physical therapist experienced in neurorehabilitation, who was not involved in data analysis or outcome evaluation.

Evaluation Criteria

Treatment efficacy was assessed at two time points: baseline (prior to BTX-A injection) and six months post-injection. The following standardized clinical instruments were employed to evaluate motor function, spasticity, and muscle strength:

Motor Function: Assessed using the Brunnstrom Recovery Stages, with separate scoring for the hand and upper extremity. This scale provides a stage-based evaluation of motor recovery following stroke, ranging from flaccidity (Stage I) to near-normal movement patterns (Stage VI).

Spasticity: Evaluated using the Modified Ashworth Scale (MAS), which quantifies resistance during passive soft-tissue stretching. The MAS scores range from 0 (no increase in muscle tone) to 4 (rigid in flexion or extension), offering a reliable measure of spasticity severity.

Overall Motor Performance: Measured with the Fugl-Meyer Assessment for Upper Extremity (FMA-UE), a validated and widely used tool that evaluates motor function, coordination, and

reflexes in the paretic arm. Scores range from 0 to 66, with lower scores indicating more severe impairment.

Muscle Strength: Quantified using a handheld dynamometer (Jamar® or equivalent) for both the paretic and non-paretic upper extremities. Grip strength (in kilograms) was recorded as the maximum value of three consecutive trials, with standardized positioning to ensure consistency.

All assessments were conducted by a trained physiotherapist ([name]) blinded to group allocation. Standardized testing protocols were followed across all time points to ensure inter-session reliability.

Intervention Protocol

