All participants initiated their rehabilitation and mirror/sham therapy sessions two weeks after the BTX-A injection, coinciding with the onset of the toxin's maximal clinical effect. Adherence to the intervention protocol was strictly monitored throughout the study period.

Statistical Analysis

All statistical analyses were performed using IBM SPSS Statistics for Windows, Version 22.0 (IBM Corp., Armonk, NY, USA). The normality of continuous variables was assessed using the Shapiro-Wilk test. As the data were not normally distributed, non-parametric tests were employed for all comparisons. Continuous variables were expressed as mean \pm standard deviation (SD), and categorical variables were presented as frequencies and percentages. Between-group comparisons at baseline and post-treatment were conducted using the Mann-Whitney U test for continuous variables and the Chi-square test for categorical variables. To evaluate within-group changes from pre- to post-treatment, the Wilcoxon signed-rank test was used. In addition, Spearman's rank-order correlation coefficient (ρ) was calculated to assess the relationships between changes in motor function, spasticity, and muscle strength. A two-tailed p-value < 0.05 was considered statistically significant for all analyses. No corrections for multiple comparisons were applied, as the primary outcomes were pre-specified.

A priori sample size estimation was performed using G*Power software (Version 3.1), assuming a two-tailed test with an effect size of $d = 0.62$, $\alpha = 0.05$, and power $(1-\beta) = 0.80$. A minimum total sample size of 28 participants (13 in one group and 15 in the other) was deemed sufficient to detect statistically meaningful between-group differences.

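### Multiplicity correction is waived because the primary outcomes were pre-specified, but that alone does not control familywise error, and these documents name no primary outcome, testing order or all-must-succeed rule

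*Combined protocol and SAP*

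**What the plan says.** The Statistical Analysis section applies a two-sided 0.05 threshold to every analysis and then adds: "No corrections for multiple comparisons were applied, as the primary outcomes were pre-specified". The plural is the authors' own. The word primary appears nowhere else in the documents.

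Study Design and Participants gives the aim as "to investigate the combined effects of Botulinum Toxin Type A (BTX-A) and Mirror Therapy (MT) on upper extremity spasticity in stroke patients", but designates no measure as primary. Evaluation Criteria introduces its list with "The following standardized clinical instruments were employed to evaluate motor function, spasticity, and muscle strength" and does not rank the entries. The list is:
- Brunnstrom stages, "with separate scoring for the hand and upper extremity"
- MAS
- FMA-UE
- grip strength, measured on both the paretic and non-paretic sides

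The sample size paragraph does not tie d = 0.62 to any of these.

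Two statements in Study Design and Participants matter for the remedy. One refers to a protocol that is not reproduced here: "The study was conducted according to the approved protocol and completed as planned without early termination". The other places the end of data collection in the past: "all post-treatment evaluations were completed by March 2025".

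**The concern.** The sentence gives a reason for not correcting, and the reason does not do that work. A single primary outcome, a fixed testing order, a split of alpha or a requirement that all primaries succeed would each control the error of an overall claim. Naming several outcomes in advance and testing each at 0.05 does not.

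This matters only if one significant outcome can carry the overall conclusion. Nothing in these documents prevents that. If one result below 0.05 were presented as showing that mirror therapy works, the nominal 5% would not apply to that claim, and the stated reason would tell readers that no adjustment was needed.

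**Working it through.** **The plan's own figure.** The documents state no familywise error rate, so there is none to reproduce. The planned total of 28 does not follow from d = 0.62 with 80% power (a two-sided t-test needs 42 per arm), but that is a separate matter. Only d = 0.62 and the analysed 15 per arm are used below.

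**Inputs.**
- Two-sided 0.05 per test, no correction (Statistical Analysis).
- 15 per group analysed (Study Design and Participants).
- Two time points, baseline and six months, so one post-treatment between-group test per outcome (Evaluation Criteria).
- Number of outcomes m: Brunnstrom hand, Brunnstrom upper extremity, MAS, FMA-UE and paretic grip make five. Non-paretic grip, if it is an efficacy outcome, makes six.
- Correlation between outcomes: not given. A common value is assumed and varied.

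**The count is a reading.** The inclusion criterion speaks of one score, "Modified Ashworth Scale (MAS) score between 1 and 4 in the affected upper extremity", while Evaluation Criteria uses the plural: "The MAS scores range from 0 (no increase in muscle tone) to 4 (rigid in flexion or extension". Neither names a joint or muscle. MAS is counted once here, and m would be larger if several joints were analysed. It would be smaller if only some of the outcomes are the intended primaries.

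**Independent tests.** The chance of at least one false positive is 1 - 0.95^m:
- m = 2: 1 - 0.95^2 = 9.75%
- m = 3: 1 - 0.95^3 = 14.3%
- m = 5: 1 - 0.95^5 = 22.6%
- m = 6: 1 - 0.95^6 = 26.5%

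**Correlated tests.** These are simulated Mann-Whitney tests with 15 per arm, equicorrelated normal outcomes and 200,000 runs. Each cell gives the result without / with continuity correction.

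| Correlation | Five outcomes | Six outcomes |
|---|---|---|
| 0 | 22.8% / 20.7% | 26.7% / 24.3% |
| 0.5 | 19.0% / 17.4% | 21.7% / 19.9% |
| 0.9 | 10.9% / 10.0% | 11.8% / 10.8% |
| 1 | 5.0% / 4.5% | 5.0% / 4.5% |

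**Ordinal scales.** Both Brunnstrom scores and MAS are short ordinal scales. They were cut to 6, 6 and 5 categories with assumed shares of 5/20/30/25/15/5% (Brunnstrom) and 5/25/35/25/10% (MAS). By Mann-Whitney, five outcomes then give 18.9% / 17.8% at 0.5 and 11.5% / 10.8% at 0.9, much as before. At perfect latent correlation the figure is about 7%, not 5%, because the cut scales do not reject in exactly the same samples as the continuous ones.

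**If the ordinal scales went to Chi-square.** The section assigns Chi-square to categorical variables and does not say which outcomes those are. Under the same assumed shares, five outcomes give 18-19% (independent), 17% (0.5) and 14% (0.9). Six give 21-23%, 20-21% and 15%.

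**Power cost of correcting.** Holm's first threshold is 0.05/m: 0.05/5 = 0.01 and 0.05/6 = 0.0083. At d = 0.62 and 15 per arm, t-test power per outcome is 37% at 0.05, 16% at 0.01 and 15% at 0.0083. The d detectable with 80% power rises from 1.06 to 1.33 (five) or 1.36 (six).

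Baseline tests, within-group Wilcoxon tests and Spearman correlations are not counted in any of these figures.

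**The case against.** Four points on the other side have weight.

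*Each outcome may support its own separate claim.* Testing each at 0.05 is then defensible, and the documents state no win criterion. This stands as a condition on the point. It does not rescue the sentence, which offers pre-specification as the reason.

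*The primaries may be recorded elsewhere.* These documents read as a retrospective account, and the approved protocol is not supplied. The aim concerns spasticity and MAS is the only spasticity instrument, so a single primary is conceivable, though the plural wording weakens that. A reader might infer that no primary was ever specified. The documents do not support this; they show only that none is named here. If one was recorded, its own test has a 5% error rate.

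*The outcomes are correlated.* Most come from the same paretic arm, so independence is unlikely. A reader might take 23% or 26% as this trial's actual error rate. That is not supported: those figures are upper ends for five and six outcomes, and the true correlation is unknown. The opposite inference, that strong correlation removes the problem, also fails. At 0.9 the rate is still about twice nominal, and it nears 5% at perfect correlation only if every outcome is continuous.

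*The lack of correction is openly disclosed.* It is, and that disclosure should stay. Only the justification attached to it is wrong.

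Nor can a reader infer that any particular finding is a false positive. The documents report no outcome results.

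**Conclusion.** The point holds as a defect in a stated rule. Confidence is high that the reason does not justify the waiver and that no primary outcome, order or all-must-succeed rule appears in these documents. It is a should-fix matter, because wording and reanalysis resolve it.

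The size is conditional. It assumes that any one outcome can carry the claim, that the family is five or six post-treatment between-group Mann-Whitney tests with MAS counted once, and that one common correlation applies. On that basis the false-positive chance is about 10-22% for correlations of 0.5 to 0.9. The lower limit at perfect correlation is about 5% if all outcomes are continuous, or about 7% with three short ordinal scales under the assumed category shares.

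**What to change.** Delete the clause giving pre-specification as the reason, and keep the statement that the original analysis was uncorrected. Then look for a dated record from before data review.

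- **It names one primary outcome:** that outcome alone carries the efficacy claim, at 0.05.
- **It names several:** apply Holm across them, unless the same record requires all to succeed, in which case each is tested at 0.05.
- **No such record exists:** do not choose a primary now, since data collection is over. Take one of two routes:
  - Report Holm-adjusted (or permutation step-down) p-values beside the unadjusted ones across all m post-treatment between-group comparisons. State m, counting every MAS score analysed, and counting non-paretic grip unless an earlier record makes it a reference only. Label the adjustment as added after data collection, and base any overall efficacy claim on the adjusted values.
  - Label all outcomes exploratory, report estimates with intervals, and make no confirmatory claim.

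In every case, label the within-group tests and correlations as descriptive.

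No new data are needed. The price is the loss of power shown above, so a non-significant adjusted result must not be read as evidence of no effect. Holm is also conservative under strong correlation (actual error about 2% at 0.9), which is the case for the permutation method. Adjustment among completers does not remove any bias from the 43 - 30 = 13 randomised patients left out of the analysis.

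### The planned total of 28 does not follow from d = 0.62, two-sided alpha 0.05 and 80% power: a two-sample t-test needs 84, and 13 versus 15 gives about 35% power

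*Combined protocol and SAP*

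**What the plan says.** The last paragraph of the Statistical Analysis section reports an a priori calculation in G*Power 3.1, "assuming a two-tailed test with an effect size of $d = 0.62", alpha 0.05 and "power $(1-\beta) = 0.80". Its result is: "A minimum total sample size of 28 participants (13 in one group and 15 in the other) was deemed sufficient". The stated purpose is to detect differences between the two groups. The paragraph does not name the test family, the outcome or the source of d, and it mentions no baseline correlation, covariate adjustment or dropout allowance.

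The same section gives the analysis: "Between-group comparisons at baseline and post-treatment were conducted using the Mann-Whitney U test for continuous variables". The reason offered is: "As the data were not normally distributed, non-parametric tests were employed for all comparisons".

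The participant flow in Study Design and Participants reports "22 patients in the Mirror Therapy (MT) group and 21 patients in the Sham Therapy (SHA) group" at randomisation. Of these 43, 30 were analysed: "15 participants in each group (n = 30 total) completed the full 6-month intervention".

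**The concern.** A standardised difference of 0.62 is moderate, and a two-group comparison with about 14 per group is normally powered only for effects above one standard deviation. The stated inputs and the stated size therefore look incompatible.

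This paragraph is the only justification given for the size of the trial. A reader who accepts it will believe that the study had an 80% chance of detecting an effect of 0.62 SD, and may take a non-significant group difference as evidence against such an effect. If the real power is less than half the stated figure, that inference fails.

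**Working it through.** **Inputs, all from the Statistical Analysis section:** d = 0.62 (so SD = 1), two-sided alpha 0.05, power 0.80, groups of 13 and 15. The 15/15 analysed and the 22/21 randomised come from the participant flow.

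**Step 1. Try to reproduce 28 with a two-sample t-test.**

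Normal approximation, per group: n = 2(z₀.₉₇₅ + z₀.₈₀)² / d² = 2(1.960 + 0.842)² / 0.62² = 40.8, so 41 per group.

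Noncentral t, as used for an exact t-test calculation: n = 41.8 per group. Checking whole numbers, 41/41 gives 79.2% and 42/42 gives 80.2%. The requirement is 42 per group, 84 in total. Keeping the 13:15 ratio gives 39.0 + 45.0, again about 84 before rounding up. The figure of 28 is not reproduced.

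**Step 2. Power at the sizes in the documents.**

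Noncentrality = d·√(n₁n₂/(n₁+n₂)), compared with the two-sided critical t on n₁+n₂−2 degrees of freedom. For 13/15: 0.62 × √(195/28) = 1.636 against a critical value of 2.056.

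| Groups | t-test power at d = 0.62 | d detectable with 80% power |
|---|---|---|
| 13/15 (planned) | 35.1% | 1.10 |
| 15/15 (analysed) | 37.5% | 1.06 |
| 22/21 (randomised) | 51.0% | not computed |
| 42/42 | 80.2% | about 0.62 |

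The ratio 1.06/0.62 is 1.7. At 15/15 a true effect of 0.62 would be missed in 100 − 37.5 = 62.5% of trials.

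**Step 3. Other readings of the stated inputs.**

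- One-sided t-test: 33 per group (66 in total). Power at 13/15 is 47.9%.
- Paired t-test: 23 in total. A signed-rank test at its minimum relative efficiency needs 26. Both test change within one set of patients, so neither yields groups of 13 and 15 or serves the stated between-group purpose.
- Repeated-measures interaction with f = 0.31 and an assumed correlation of 0.5: 23 in total.
- Baseline-adjusted comparison (ANCOVA): 28 is reached only if the correlation between baseline and follow-up is assumed to be about 0.82. The plan states no correlation and contains no ANCOVA.

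**Step 4. The planned Mann-Whitney test.**

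Its power depends on the shape of the data, which the plan does not specify, so the shapes below are assumptions. Each is a 0.62 SD shift, two-sided 0.05, by simulation (40,000 runs for power, 20,000 for required size).

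| Assumed shape | Power 13/15 | Power 15/15 | n per group for about 80% |
|---|---|---|---|
| Normal | 32% | 34% | 44 |
| Laplace | 44% | 46% | 32 |
| Exponential | 57% | 60% | 24 |

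For these three shapes the total runs from 48 to 88. Those figures are not outer limits. At the minimum relative efficiency of the test the total is 98. In the other direction, a very long-tailed log-normal (sigma 1) reached 84% at 13/15. For five- or six-level ordinal scores cut from normal data, the kind of short scale that MAS and the Brunnstrom stages are, power was 32–33% at 13/15 and 34–35% at 15/15.

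**The case against.** The strongest reply is that the plan names no test family, so the figures of 84 and 35% rest on a t-test chosen in this review, whereas the planned test is Mann-Whitney on data said to be non-normal. Under a long-tailed log-normal shape that test does reach 80% with 28 patients. A misprinted d, an unstated baseline correlation, or a per-group figure reported as a total could also lie behind the number. On the last possibility, the asymptotic Mann-Whitney size for Laplace data is 28 per group.

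Part of this stands. The documents do not show which element is wrong, and the Mann-Whitney requirement has no single value. It does not rescue the statement as written. The remark on non-normality describes the data once collected and is not a planning assumption. No log-normal shape, correlation or covariate adjustment is stated. On short ordinal scales such as MAS and Brunnstrom, the simulated power stays near one third.

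It can also be said that the trial is finished, that 15/15 exceeds the stated minimum, that no estimate or p-value changes, and that the documents do not themselves interpret a non-significant result. All of that is true, and it limits the consequence to the power statement and how results are read. Exceeding a minimum is no reassurance when the minimum does not follow from its inputs.

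**Conclusion.** The concern holds: the statement is wrong as written. With the stated d, alpha and power, a two-sample t-test needs 84 patients, three times the stated 28. Power is 35% at 13/15 and 37% at 15/15, against 80% claimed. The planned Mann-Whitney test does no better with normal data (about 88 in total, 32% power at 13/15) and still falls short under the Laplace and exponential shapes tried. The t-test figures assume normal data with equal variances; the Mann-Whitney figures assume a pure location shift of 0.62 SD. The conclusion that 28 does not follow from the stated inputs would change only with an input that the plan does not give.

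**What to change.** Retrieve the saved G*Power inputs and check the test family, the outcome, the source of d, and whether 28 was per group or in total. Correct whichever element is wrong.

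If d = 0.62 stands, replace the claim that 28 is enough with wording such as:

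> For d = 0.62, two-sided alpha 0.05 and 80% power, a two-sample t-test requires 42 participants per group. With 15 per group analysed, power at this effect is about 37% by t-test. For the Mann-Whitney test it is about 34% if the data are normal, and higher for some non-normal shapes. The effect detectable with 80% power by t-test is about d = 1.06 (1.10 with 13 and 15).

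If another input was misprinted, state the corrected inputs, the test and the size they give.

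As separate good practice, report the between-group result as an estimate with a 95% confidence interval, and do not present non-significance as absence of effect.

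The cost is one check of saved settings and a few sentences. No added enrolment and no change of test or outcome is needed. If d = 0.62 stands, the corrected power statement will be less favourable than the present one.
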